A multi-center, prospective, randomized study comparing surgical and economic parameters of Total Knee Replacement performed with single-use Efficiency instruments with patient-specific technique (MyKnee®) versus traditional metal instruments with conventional surgical technique.

### **1.1 Study Rationale**

Total knee arthroplasties are a common procedure in the United States (US), designed to relieve pain and improve the quality of life in patients with advanced knee osteoarthritis. Age and obesity are major risk factors for osteoarthritis and as the US population continues to age and body mass index (BMI) levels increase, the incidence of total knee arthroplasties will increase as well. In 2013, total knee arthroplasties were occurring at a rate of greater than 500,000 procedures per year and are expected to increase to 3.48 million by 2030. Costs for total knee arthroplasties currently exceed \$11 billion in the US alone.

With the numbers of total knee arthroplasties continuing to increase, efforts are being made to cut procedural costs. One way this can be achieved is by decreasing operative times. The utilization of single-use instruments can decrease the time spent preparing for and cleaning after the surgery, thereby decreasing patient turnover time. Single-use instruments are common in ophthalmology, cardiothoracic surgery and urologic surgery, but have yet to experience much of a crossover into lower extremity surgery, including total joint arthroplasty. Mont *et al.* studied 400 procedures using single-use instruments for total knee arthroplasty, concluding that single-use instruments showed promising benefits and after further study, could play a role in increasing operating room efficiency. Siegel *et al.* found that total operating room time during total knee arthroplasty was on average 30 minutes shorter for single-use instruments and saved between \$480 and \$600 per case. The same study also suggested that single-use instrumentation may also decrease the risk of infection. There is controversy regarding some manufacturers' claims of improved clinical outcomes, surgical efficiency and decreased costs with patient-specific cutting blocks. It is evident that not all patient-specific instruments from different manufacturers are equivalent, and each needs to be studied individually. This study is being conducted to evaluate the total knee replacement instrument options for a single manufacturer.

### **1.2 Study Treatment**

The GMK single-use (Efficiency) instruments are made of medical-grade composite technopolymers that give high fatigue and abrasion resistance in addition to form versatility. The single-use instruments are shipped from the manufacturer in pre-sterilized packaging, eliminating the need to use the hospital Central-Sterile processing equipment. The reproducible sterility may potentially reduce the infection risk.

---

 Losina E, *et al.* Cost-effectiveness of Total Knee Arthroplasty in the United States: Patient Risk and Hospital Volume. *Arch Intern Med* (2009); 169(2):1113-1122.

 Mont MA, *et al.* Single-Use Instruments, Cutting Blocks, and Trials Increase Efficiency in the Operating Room During Total Knee Arthroplasty: A Prospective Comparison of Navigated and Non-Navigated Cases. *J Arthroplasty* (2013); 28(7):1135-1140.

 Siegel Gw, *et al.* Cost Analysis and Surgical Site Infection Rates in Total Knee Arthroplasty Comparing Traditional vs. Single-Use Instrumentation. *J Arthroplasty* (2015); 30: 2271-2274

 Lachiewicz, PF, Henderson, RA: Patient-specific Instruments for Total Knee Arthroplasty. *J Am Acad Orthop Surg*, 2013; 21:513-518.

MyKnee® patient-specific cutting blocks allow the surgeon to realize his pre-operative 3D planning, based on CT or MRI images of the patient's knee. The blocks are created based on the individual patient's anatomy, his/her mechanical axis, and the surgeon's preferred reconstruction goals. The innovative concept combines the following features giving potential benefits to both the surgeon and the patient:

- Accurate bony cuts and therefore implant positioning
- No intramedullary canal violation
- Up to 60% reduction of surgical steps for bone resection and related time
- Up to 66% reduction of time and cost in washing, assembling and sterilization procedures
- Interactive 3D web planning

### **1.3 Study Objectives**

The objectives of this study are to compare economic factors and the rate of adverse events between two types of instrumentation used for total knee replacement:

- Single-use Efficiency Instruments with Patient Specific Technique (MyKnee®)
- Traditional Metal Instruments with Conventional Surgical Technique

The data obtained from this study could be useful for surgeons, facilities, and payors to help determine appropriate instrumentation in total knee arthroplasties.

#### **Primary Objective:**

- To compare the time-saving parameters associated with the two procedures with respect to parameters such as OR preparation time, intra-operative time (OR efficiency), OR clean-up time and sterilization costs.

#### **Secondary Objectives:**

To compare the following surgical and clinical outcomes between the two study groups

- To compare correction of alignment after total knee replacement via long standing AP hip-knee-ankle x-rays.
- To compare the accuracy of tibial slope angle on a lateral knee x-ray
- To compare the number of trays sent to sterilization
- To compare the volume of estimated blood loss during the procedure
- To compare the drop in post-operative (day 1) hemoglobin and total volume of transfusions (allogeneic and/or autologous)
- To compare the occurrence of adverse events
- To compare the waste weight at the end of each surgery, considering separately those recyclable and those not recyclable.
- To compare the rate of intraoperative and post-operative complications
- To compare the rate of successful use of MyKnee® cutting blocks (i.e. the incidence of surgical cases where the surgeon did not need to abort the use of MyKnee intra-operatively and default to the use of standard cutting blocks).

The cost-per-minute value based on hospital estimates will be used to calculate an overall cost-savings total.

## 2

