### **STUDY DESIGN**

The study is a multi-center, prospective, randomized study comparing surgical and economic parameters of Total Knee Replacement performed with single-use Efficiency instruments with patient-specific technique (MyKnee®) versus traditional metal instruments with conventional surgical technique. The objective is to evaluate the impact of single-use instrumentation versus traditional metal instruments in reducing overall surgical costs and improving mechanical axis alignment. The timing of routine surgical phases will be measured, including the pre-operative preparation time, intra-operative phase, OR clean-up time and sterilization phase in 300 adult patients undergoing total knee replacement. AP and lateral x-rays will be utilized to assess the implant's mechanical axis alignment and tibial slope after discharge to the completion of the 6 week visit. Additionally, other parameters will be recorded including blood loss, post-op day 1 hemoglobin drop, adverse events, number of trays sent to sterilization, and total waste weight at the end of each procedure, considering separately those recyclable and those not recyclable. To ensure that the minimum of 300 patients is met, 342 patients will be randomized into two treatment cohorts in a 2:1 ratio.

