#### **Group B: Traditional Metal Instruments with Conventional Surgical Technique (Conventional TKA)**

Patients randomized to Group B will undergo conventional surgical technique utilizing traditional metal instrumentation and traditional cutting blocks (Metal)

Additional demographic information will be collected to describe the study population and to document whether the two treatment groups are clinically comparable. Data collected will include: age, gender, BMI, race/ethnicity, smoking history, and employment status, in addition to pre-operative knee history/diagnosis and degree of pre-operative knee malalignment and Kellgren-Lawrence grade.

## 3

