### STATISTICAL ANALYSIS PLAN

The Sponsor will evaluate for non-inferiority based on economic factors and the rate of adverse events between the two groups. The Sponsor may conduct additional post-hoc analyses of the study data after study completion. These analyses may be done for the purposes of publication or in conjunction with additional data that may be available to Sponsor from other sources.

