#### **4.1 Data Analysis**

The objectives of this study are outlined in Section 1.3. For purposes of this study, economic outcomes of interest include the peri-operative time, intra-operative time (OR efficiency), and sterilization times as quantitative values. These outcomes will be subsequently used in comparative cost analyses. The secondary objectives are to assess the accuracy of mechanical axis alignment and posterior tibial slope after total knee replacement, additional operative parameters, and adverse events.

Descriptive statistics, specifically means will be used to summarize the peri-operative, intra-operative and sterilization time data.

The primary objective will be met by comparing mean values of each of the time-saving parameters. The null hypotheses of no differences in mean values between re-usable and single-use devices will be tested using separate t-tests for two independent groups for each endpoint. A p-value of less than 0.05 will be considered significant for each endpoint. Endpoints with statistically significant differences are expected to contribute to expected cost differences to be determined in subsequent analyses.

Descriptive analyses as well as similar two-sample comparisons will be used to evaluate secondary measures.

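### The plan calls its cost result an overall saving, but the only price it specifies is a rate per minute; no non-time resource that differs between the arms is priced

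*Combined protocol and SAP*

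**What the plan says.** The costing rule is one sentence at the end of the secondary objectives in section 1.3: "The cost-per-minute value based on hospital estimates will be used to calculate an overall cost-savings total". Section 2 (Study Design) states the aim more broadly, to "evaluate the impact of single-use instrumentation versus traditional metal instruments in reducing overall surgical costs".

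Section 4.1 describes the economic outcomes as peri-operative, intra-operative and sterilization times, and says "These outcomes will be subsequently used in comparative cost analyses". Later in the same section it adds: "Endpoints with statistically significant differences are expected to contribute to expected cost differences to be determined in subsequent analyses".

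Three places touch on other cost inputs:

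- The primary objective in section 1.3 gives examples of time-saving parameters that end with "intra-operative time (OR efficiency), OR clean-up time and sterilization costs".
- Section 4.2 explains the increase from 300 to 342 patients partly by further economic analyses.
- The opening of section 4 allows post-hoc analyses, possibly "in conjunction with additional data that may be available to Sponsor from other sources".

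The arms differ in what they consume. On Group A's instruments, section 1.2 says: "The single-use instruments are shipped from the manufacturer in pre-sterilized packaging". Section 3.2 has the cutting blocks custom-made for Group A. Group B uses reusable metal instruments and traditional blocks (section 2). The visit schedule in section 3.4 lists a planning CT or MRI for Group A only, although section 3.2 describes planning imaging as standard of care in both arms. Section 3.3 records the number of trays and the waste weight.

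**The concern.** A figure presented as an overall saving should net off everything that differs between the arms. Here the single-use set and custom blocks are part of how Group A is meant to save time, yet the written rule values only the minutes. Group B has unpriced items too: the metal set and its reprocessing.

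Section 1.3 says the data could help surgeons, facilities and payors choose instrumentation. Those readers need the net cost per case. A minutes-based total under an overall label could be taken for that net cost when neither its sign nor its size is known.

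**Working it through.** **1. What is priced.** Each resource set against the text:

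| Resource | Where it appears | Price or costing method |
|---|---|---|
| Operating-room and sterilization minutes | 3.3, 4.1 | Hospital cost per minute (1.3); no value given, and no statement whether one rate covers both kinds of minute |
| Single-use set (A) | 1.2, 2 | None |
| Custom cutting blocks (A) | 1.2, 3.2 | None |
| Planning CT or MRI (A), other planning imaging (B) | 3.2, 3.4 | None |
| Metal instrument set (B) | 2 | None |
| Sterilization | Named as a cost in 1.3; recorded in 3.3 and carried into 4.1 as times | None beyond minutes |
| Trays, waste weight | 1.3, 3.3 | Count and grams; none |

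Only the first row can be turned into money with what is written.

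**2. What the missing rows can do.** Let T be the time-priced saving per case and D Group A's net extra non-time cost per case (negative if Group B's items cost more). Then

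net saving = T − D = T × (1 − D/T).

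For assumed D/T of −0.5, 0, 0.5, 1 and 1.5, the net is 1.5T, T, 0.5T, 0 and −0.5T. This is algebra. The documents do not say where the trial lies in that range.

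**3. Scale of T.** The pooled planning differences in the section 4.2 table are 6.737 for set-up plus clean-up and 5.893 for surgical episode time. The table gives no unit; I take minutes and assume the intervals do not overlap:

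6.737 + 5.893 = 12.63 minutes.

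The plan gives no cost per minute. The background in section 1.1 cites 30 minutes and $480 to $600 saved per case. If that whole saving were time, the rate would be 480/30 = $16 to 600/30 = $20. Then

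- 12.63 × 16 = $202 and 12.63 × 20 = $253 per case;
- surgical episode time alone: 5.893 × 16 = $94 and 5.893 × 20 = $118.

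At an assumed $100 per minute, 12.63 minutes come to $1,263. These are break-even values: if D exceeds them, a time-only saving is a net loss. No value of D is available. Sterilization time is not in the planning table and so is not in these figures.

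**4. Sample size and precision.** The plan's own figure reproduces. For set-up time (difference 2.985, SD 8.66, two-sided 0.05, 80% power, 2:1), the normal approximation gives 100 controls and a total of 300. The t-test calculation gives 298.7. Then 300 × 1.14 = 342. No cost quantity enters this calculation.

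With every phase retained, the precision of the 12.63-minute total at 228:114 is as follows:

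- SD = √(14.63² + 16.79² + 2ρ × 14.63 × 16.79), which is 22.27 at ρ = 0 and 27.23 at ρ = 0.5 (ρ is assumed).
- SE = SD × √(1/228 + 1/114) = SD × 0.1147, which is 2.55 to 3.12.
- 95% half-width = 1.967 × SE, which is 5.02 to 6.14 minutes.

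A time-related difference over all these phases can therefore be reported with an interval from the planned sample.

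**The case against.** The strongest reply is that the plan never says minutes are the only input. Section 1.3 says the rate will be used, not that nothing else will be. Section 4.1 says the economic outcomes include times, the primary objective names sterilization costs among examples, and sections 4.1 and 4.2 defer further economic work. A per-tray cost may well be intended. This stands to the extent that the plan cannot be said to exclude non-time costs. But room for an input is not a specification of it: no item, source or method is given. The sponsor data mentioned in section 4 belong to post-hoc work.

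Some listed items are also less certain than others. Section 3.2 gives both arms standard-of-care planning imaging, so a difference in imaging cost is possible but not established. Section 2 says only that Group B uses metal instruments; that the set has a cost per case is an inference, though a modest one.

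A reader might infer that the total must overstate the benefit of Group A. The documents do not support that, because both arms have unpriced items and no unit cost is given.

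A reader might also infer from the second section 4.1 sentence that only significant phases are costed. It says such endpoints are expected to contribute, which is not a stated filter, and the same section sends the time outcomes generally into the cost analyses. Purely as a hypothetical, a p < 0.05 filter at the planning effects would lower the average 12.63-minute total to 11.90 (about 6%) and raise its standard deviation across trials by 31% to 35%. The pricing point does not rest on this.

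Finally, the total carries no hypothesis, alpha or sample size. That limits the severity but does not correct the label.

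**Conclusion.** The point holds as a gap between label and specification. As written, the only total that can be calculated is a time-related cost difference, while the plan presents it as overall and aims at overall surgical costs. The direction and size of the net difference cannot be told from the documents. The only scale available is the break-even: $202 to $253 per case for 12.63 minutes, resting on the assumed $16 to $20 per minute, on minutes as the table's unit and on non-overlapping phases.

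It should be fixed before analysis because of the use described in section 1.3. It does not touch the primary time comparisons or N = 342.

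**What to change.** In section 1.3, choose one of two options:

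- Rename the result *time-related cost difference (excludes instrument, cutting-block, imaging and reprocessing costs)*, draw no conclusion about overall cost from it, and bring the aim in section 2 into line.
- Before analysis, fix a list of non-time unit costs for both arms on the same basis, and report the net cost difference per case with a 95% confidence interval. For Group A: the single-use set, the cutting blocks and any difference in planning imaging. For Group B: the metal set per case and its reprocessing, so far as this is not already in the sterilization rate.

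In section 4.1, replace the sentence on statistically significant endpoints with: *All measured time phases enter the cost difference whatever their p-values; minutes that overlap between phases are counted once, and OR and sterilization minutes are each priced at their own stated rate.* The overlap clause is needed because section 3.3 gives no start and stop points showing that the phases are separate.

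Renaming costs a few words. The fuller option needs a short price list agreed by the sponsor and hospitals before analysis, and the reported saving may be smaller. Neither needs extra patients, visits or procedures.

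### The overall cost saving is planned as a bare total: no per-patient cost, estimator, interval, test or margin is specified for it

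*Combined protocol and SAP*

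**What the plan says.** Section 2 (Study Design) gives the objective as evaluating the effect of single-use instruments "in reducing overall surgical costs and improving mechanical axis alignment". Section 1.3, at the end of the secondary objectives, supplies the only cost calculation: "The cost-per-minute value based on hospital estimates will be used to calculate an overall cost-savings total".

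Section 4.1 defines the economic outcomes as times: "economic outcomes of interest include the peri-operative time, intra-operative time (OR efficiency), and sterilization times as quantitative values". It then adds: "These outcomes will be subsequently used in comparative cost analyses". The time data are to be summarised by means. The hypotheses are "tested using separate t-tests for two independent groups for each endpoint", and "A p-value of less than 0.05 will be considered significant for each endpoint". The link from these tests to cost is: "Endpoints with statistically significant differences are expected to contribute to expected cost differences to be determined in subsequent analyses".

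The opening paragraph of Section 4 also announces a non-inferiority evaluation on economic factors and adverse events, without a margin or a cost variable. Section 4.2 bases the sample size on four time endpoints. Part of the 14% increase is meant to leave room for further economic analyses, but no cost effect, standard deviation or power is given.

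**The concern.** Followed as written, the plan produces a set of phase-level mean differences, each with its own p-value, and then one cost figure built from them. No step gives that figure a standard error. The phase tests do not contain one: the variance of a sum of phases timed on the same patient depends on the covariances between phases, and separate t-tests do not estimate these.

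Section 4.1 also ties the cost difference to phases that reach significance. If only those phases enter, real but non-significant differences are set to zero and the total is biased as well as unqualified.

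Section 1.3 says that surgeons, facilities and payors may use the results to choose instrumentation. They would receive a saving per case with no means of telling how far it could be from the truth, or whether it differs from zero.

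**Working it through.** **1. The plan's own figure.** The sample size is driven by set-up time, with effect size 2.985 / 8.66 = 0.345. For 2:1 allocation, two-sided 0.05 (sidedness is not stated; two-sided assumed) and 80% power:

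- control n = (1.96 + 0.8416)² × (1 + 1/2) / 0.345² = 98.9, so 99 and a total of 297. The t-test calculation gives 298.7. The stated 300 reproduces.
- 300 × 1.14 = 342, that is 228:114. Power for set-up time is then about 85%.

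This power belongs to single time endpoints. No cost quantity enters it.

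**2. What an interval on a total would look like (illustration).** Inputs are the pooled rows of the Section 4.2 table:

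| Row | Difference (min) | SD (min) |
|---|---|---|
| Combined (set-up plus clean-up) | 6.737 | 14.63 |
| Surgical episode time | 5.893 | 16.79 |

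Assumptions: the two times do not overlap, all 342 patients contribute, and the within-patient correlation r is 0 to 0.5.

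- Total = 6.737 + 5.893 = 12.63 min.
- SD of total = √(14.63² + 16.79² + 2r × 14.63 × 16.79).
- Standard-error factor = √(1/228 + 1/114) = 0.1147.
- Half-width = 1.967 × 0.1147 × SD (t multiplier on 340 degrees of freedom).

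| r | SD | SE | Half-width | Share of 12.63 | 95% interval |
|---|---|---|---|---|---|
| 0 | 22.27 | 2.55 | 5.0 | 40% | 7.6 to 17.7 |
| 0.5 | 27.23 | 3.12 | 6.1 | 49% | 6.5 to 18.8 |

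At the extreme r = 1 the half-width is 7.1 min (5.5 to 19.7). The interval excludes zero throughout. The width nevertheless changes with r, which the separate phase tests do not provide.

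**3. What happens if only significant phases are added.** Take set-up, clean-up and surgical episode as three phases at 228:114, again assuming no overlap. For a phase with true difference d, standard error s and z = d/s, the expected contribution is d × P(significant) + s × [φ(1.96 − z) − φ(−1.96 − z)]. Expectations add whatever the correlation between phases.

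| Phase | s | At full planning effect | At half effect |
|---|---|---|---|
| Set-up | 0.99 | 2.77 of 2.985 | 0.84 of 1.49 |
| Clean-up | 1.11 | 3.62 of 3.752 | 1.16 of 1.88 |
| Surgical episode | 1.93 | 5.51 of 5.893 | 1.68 of 2.95 |
| Sum | | 11.9 of 12.63 | 3.7 of 6.3 |

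A simulation with 200,000 replicates gives the same sums. The filter costs little at the planning effects and removes about 40% of the true saving at half of them (1 − 3.7/6.3).

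**4. What cannot be computed.** The documents give no cost-per-minute value, cost standard deviation or instrument acquisition cost. No cost power and no interval in currency follows from them.

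**The case against.** The plan is not silent on cost comparison. Section 4.1 announces comparative cost analyses and says that secondary measures will be evaluated by similar two-sample comparisons, and the cost sentence stands among the secondary objectives. Section 4 announces an evaluation of economic factors. A reader might infer that the cost objective will never be tested. The documents do not support that; they support only that no test of cost is specified. What remains is that a two-sample comparison needs one cost value per patient, and none is defined.

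The plan also does not say that only significant phases enter the total, only that they are expected to contribute. The bias in step 3 of the working is therefore conditional on that reading. Nor does the plan propose an interval that treats phases as independent.

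Two numerical inferences are tempting and should not be drawn:

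- *A correlation from the sample-size table.* The pooled SDs for set-up, clean-up and their sum (8.66, 9.72, 14.63) imply a correlation of about 0.26. But the SDs were back-calculated from mean differences and p-values. The same formula gives 0.87 in the non-navigated stratum (6.82, 5.96, 12.37) and −0.02 in the navigated one (10.49, 13.44, 16.87). The table says nothing usable about correlation.
- *A dollar range.* Section 1.1 cites a study with room time 30 minutes shorter and savings of $480 to $600 per case. It does not attribute the savings to those minutes, and this trial will use hospital estimates. A price per minute taken from that sentence, and limits built on it, would not be a confidence interval for this trial.

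**Conclusion.** The concern holds in this form: the trial has an overall-cost aim, and the stated route to it ends in a total with no per-patient cost, estimator, interval, test or margin. The separate phase t-tests cannot fill the gap, because the within-patient covariance is unknown.

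The size is illustrative: a half-width of 5.0 to 6.1 min on 12.6 min. It rests on the planning inputs, on SDs derived from p-values, on the assumed correlation range, and on surgical episode time excluding set-up and clean-up, which the documents do not state. Because the illustrative interval excludes zero, it does not show that a saving would be unsupported. It shows that the plan as written would report neither the width nor, if true effects are smaller, the loss of support. None of the stated sample-size figures is affected.

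**What to change.** In Sections 1.3 and 4.1:

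- Define one time-based cost per patient from a prespecified list of non-overlapping phases in Section 3.3. Patient OR time, skin-to-skin time, resection times and tourniquet time are nested and must not be added together.
- Include every listed phase, whether or not it is individually significant.
- Report the between-arm difference in mean per-patient cost with a 95% confidence interval, by unequal-variance t or by a bootstrap stratified by site (randomization is separate for each site).
- Repeat the analysis over the range of hospital cost-per-minute values.
- Claim an overall saving only if the interval excludes zero.

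The phase times are already to be recorded, so this needs plan wording and a little more programming, with no new patients or data. The drawback for the sponsor is a reported saving that looks less certain than a single total.
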